Early identification of Malignant Brain edema in laRge Artery oCclusive
stroke after Endovascular therapy (EMBRACE study)

Protocol Version Number and Date: 1.0, March 20, 2024

Background

Stroke is a significant global cause of death and disability. Endovascular thrombectomy (EVT) is currently the best treatment for acute large vessel occlusion stroke (ALVOS), as it can greatly reduce mortality and improve patient outcomes. However, only half of patients who undergo EVT achieve functional independence, and malignant brain edema (MBE), a severe complication, can occur after the procedure, leading to a poor prognosis. Previous studies have confirmed the effectiveness of early decompressive hemicraniectomy in reducing morbidity and mortality in patients with malignant brain edema. Therefore, identifying high-risk patients for MBE can help clinicians make appropriate triage and early intervention decisions, potentially saving patients' lives.

Predictive factors for post-ischemic stroke brain edema have been widely discussed, and reliable early predictive indicators have been identified, such as age, early consciousness disorders, baseline National Institutes of Health Stroke Scale (NIHSS), atrial fibrillation, hypertension, baseline blood glucose, and the level of reperfusion after EVT. Radiological factors, such as the Alberta Stroke Program Early CT Score (ASPECTS), collateral circulation rating of arteries, venous outflow status, CT perfusion core infarct volume, perfusion-based collateral status, and clot burden, are closely associated with the occurrence of MBE post-EVT. However, due to individual differences and multiple factors affecting MBE, a single factor cannot effectively predict MBE. Establishing a clinical risk prediction model can effectively identify high-risk populations for MBE at an early stage.

Aim

To design and validate a predictive model for MBE after EVT.

Design

Study Type: Observational [Patient Registry]

Time Perspective: Prospective

Study population

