All ALVOS patients will undergo comprehensive evaluation by neurologists at admission to the stroke center to obtain baseline data from clinical and laboratory examinations. Multimodality CT, including head non-contrast CT (NCCT), CT perfusion (CTP) and CTP-derived multiphase CT angiography (CTA), will be performed to assess whether patients are eligible for EVT. After EVT, all patients will be transferred to the neuro-intensive care unit for close perioperative and postoperative care to ensure stability of vital signs and implementation of comprehensive monitoring and management. This includes daily neurological assessments, monitoring of vital signs and oxygenation, and management of endotracheal intubation. Once the patient's vital signs stabilize or after the patient is extubated, they will be transferred to the neurology stroke care unit for further treatment. In principle, this trial does not involve the selection and intervention of therapeutic drugs. Within 24 hours post-EVT, patients will undergo repeat head NCCT to exclude hemorrhage and evaluate surgical outcomes. Antiplatelet therapy may be considered based on the patient's specific condition but should be cautiously selected in clinical practice and closely monitored to prevent bleeding complications. In case of signs of hemorrhagic transformation, physicians may adjust the antiplatelet therapy regimen at their discretion, potentially reducing the dose or delaying antiplatelet treatment. Additionally, regular in-hospital follow-up head NCCT scans will be performed on patients at day 3, to monitor disease progression and adjust treatment plans promptly.

Imaging protocol

Head NCCT is performed on a Toshiba Aquilion 320-slice CT scanner (Toshiba Medical Systems) using the following acquisition parameters: 120 kV, 128 mAs, scan coverage of 240 mm, and scan width of 5 mm. Simultaneously, 4-dimensional time-resolved whole-brain CTA and whole-brain CTP can be acquired. Lohexol (45 mL) (Medrad Stellant D SCT-212; Bayer Healthcare) is injected at a rate of 5

mL/second, followed by a 30 mL saline flush at an injection rate of 4 mL/second. All perfusion parameters are analyzed using post-processing software.

Radiological assessments

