The imaging variables collected in this study involve arterial, venous and perfusion status variables, including NCCT-ASPECTS, ischemic core volume, the penumbra volume, collateral status based on CTP and multiphase CTA, clot burden score, and venous outflow status. Imaging evaluations will be performed by imaging physicians who are blind to the clinical information.

CT perfusion assessment

Areas with relative cerebral blood flow (rCBF) <30% is defined as the ischemic core. The penumbra volume is calculated by subtracting the ischemic core volume (lesions with rCBF <30%) from the perfusion lesion volume (delay time threshold >3 seconds). The collateral index is defined as the volume of tissue with delay time (DT) >6 s divided by the volume with DT >2 s.

Clot burden score

We use a CBS for the anterior circulation to quantify the extent of ipsilateral intracranial thrombus, allotting major arteries 10 points for the presence of contrast opacification on CTA. Two points each is subtracted for the absence of contrast opacification in the complete cross-section of any part of the proximal M1 segment, distal M1 segment, or supraclinoid ICA, and 1 point each for M2 branches, A1 segment, and infraclinoid ICA. Partial filling defects suggesting stenosis or non-occlusive thrombus are rated as patent. A score of 10 indicates the absence of a visible occlusion on CTA, while a score of 0 indicates occlusion of all major intracranial anterior circulation arteries.

Venous outflow assessment

The outflow status of the sphenoparietal sinus, superficial middle cerebral veins, and intracerebral veins will be evaluated. Venous opacification will be graded per vein using a three-point scale based on baseline CT angiography:

- 0: Complete absence of cortical vein opacification
- 1: Moderate opacification (attenuation of one of the target veins on the contralateral side)
- 2: Full opacification.

Clinical assessments

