We will record the demographic data (gender, age, hypertension, diabetes, history of atrial fibrillation), site of occlusion, baseline systolic and diastolic blood pressure, prior IVT administration, baseline NIHSS score, NIHSS score at discharge, modified Rankin Score (mRS) at discharge, and TOAST stroke etiology (Trial of ORG 10172 in Acute Stroke Treatment) of each participant. Hematological laboratory results will include baseline glucose, baseline white blood cell count, baseline neutrophil count, baseline hemoglobin, and platelet count. The EVT operator will record the time from stroke onset to puncture (OTP), time from puncture to recanalization (PTR), and degree of blood flow restoration. The occluded vessel will be determined based on intraoperative angiography results, and reperfusion level will be graded using the modified Thrombolysis in Cerebral Infarction (mTICI) score, with complete reperfusion defined as mTICI 2b-3. Clinical assessments will be conducted by neurologists unaware of the clinical diagnosis.

Study groups

- training set

To determine potential predictive factors, imaging and clinical parameters will be enrolled into LASSO regression analysis, which effectively eliminated several irrelevant or multicollinearity independent variables to reduce high-dimensional data. The multivariable logistic regression analysis will be applied to determine the

variables predicting MBE, and the results will be used to create a predictive model based on the training set.

- validation set

The predictive model will be further validated in the validation set.

Outcome assessment

Primary Outcome Measures:

The occurrence of MBE: Patients developed MBE within 3 days post-EVT

Secondary Outcome Measures:

1. The follow-up mRS scores of enrolled patients at 90 days since stroke onset.
2. Evidence of parenchymal hemorrhage (PH type) on cranial imaging during hospitalization.

Sample size

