In this study, predictive model will be constructed using the EVT database from Zhejiang Provincial People's Hospital as a training cohort, and prospective data from other centers will be used to validate the performance of predictive model. We will randomly select 70% of the patients from the Stroke Center EVT database at Zhejiang Provincial People's Hospital as the training cohort, while the remaining 30% will constitute the internal validation cohort. Within the training cohort, our aim will be to analyze imaging and clinical parameters when constructing the predictive model.

Given the requirement of at least 10 events per candidate variable for model establishment, a minimum of 200 MBE patients is necessary in the training cohort to ensure stable model estimation. Based on a study design with a sample ratio of 7:3 for the training and internal validation sets, at least 290 MBE patients will be required in this study at Zhejiang Provincial People's Hospital. The external validation set will require 100-200 positive samples; considering an approximate 20% incidence rate of MBE in anterior circulation EVT patients, this study will need to include at least 1950 EVT patients.

Statistical analysis

Compare baseline clinical and imaging data of EVT patients with and without MBE across the training, internal validation, and external validation sets. Continuous variables conforming to a normal distribution will be described using means and standard deviations, while those not conforming will be described using medians and quartiles. Categorical variables will be expressed as percentages.

In the training set, factors influencing MBE will be analyzed. Continuous variables will be analyzed using Student's *t*-test or Mann-Whitney U test, while categorical variables will be analyzed using chi-square test and Fisher's exact test. Collinearity among variables will be assessed using Variance Inflation Factors (VIFs), where VIF <10 and Tolerance >0.1 indicate no significant collinearity. Variables with a significance level of *P* <0.1 in univariate analysis will be incorporated into logistic regression analysis using forward stepwise selection method, and odds ratios (ORs) and 95% confidence intervals (CIs) will be calculated. Factors with *P* < 0.05 will be included as independent predictors of MBE in the model. After constructing the predictive model, it will be converted into a dynamic nomogram and deployed on a webpage, generating a dynamic nomogram URL.

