The dynamic nomogram URL will be used to externally validate EVT data from other stroke centers and will collect data. The area under the receiver operating characteristic (ROC) curve (AUC) will be used to evaluate the ability of the predictive model to identify high-risk MBE patients after EVT in the training, internal and external validation sets, and corresponding 95% CIs will be calculated. Calibration plots and the Hosmer-Lemeshow goodness-of-fit test will assess the consistency between actual MBE occurrence and predicted MBE risk probability in EVT patients. Decision curve analysis (DCA) will determine the clinical net benefit of the model at different risk threshold probabilities in the three sets.

Statistical analyses will be performed using IBM SPSS Statistics software (version

26.0; IBM Corporation, Armonk, NY, USA) and R software (version 4.3.1, R Development Core Team, Vienna, Austria).

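### External validation and data collection both run through the web nomogram, and the protocol does not prevent site staff from seeing the predicted risk before MBE status is recorded

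*Protocol*

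**What the plan says.** After the model is built, the Protocol (Statistical analysis) says that "it will be converted into a dynamic nomogram and deployed on a webpage, generating a dynamic nomogram URL". It then gives that page two jobs: "The dynamic nomogram URL will be used to externally validate EVT data from other stroke centers and will collect data". The Sample size section says that "prospective data from other centers will be used to validate the performance of predictive model".

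The primary outcome (Outcome assessment) reads in full: "The occurrence of MBE: Patients developed MBE within 3 days post-EVT". No diagnostic criteria and no adjudication are given.

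Two sentences deal with masking. Under Radiological assessments: "Imaging evaluations will be performed by imaging physicians who are blind to the clinical information". Under Clinical assessments: "Clinical assessments will be conducted by neurologists unaware of the clinical diagnosis". Neither mentions the predicted risk, and neither covers the treating clinicians.

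Two passages bear on how a displayed risk might be used. The Background says that "identifying high-risk patients for MBE can help clinicians make appropriate triage and early intervention decisions". Procedures leaves care to the treating team, and the day-3 head CT is done "to monitor disease progression and adjust treatment plans promptly".

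**The concern.** External validation compares a prediction with an outcome that came about, and was labelled, independently of that prediction. Here the page that produces the prediction is also the page through which the external data arrive. If a site enters predictors soon after EVT, staff may see the risk while the outcome is still open, and two routes to bias follow.

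- **Labelling.** With no written criteria, calling MBE is a matter of judgement. An assessor who has seen a high risk may call a borderline case MBE, and one who has seen a low risk may not. The model then looks better than it is.
- **Care.** If staff act on a high displayed risk and this lowers the number of MBE events in those patients, the model looks worse and appears to over-predict.

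AUC, calibration and decision curve analysis all set predicted risk against MBE, so all three would carry the distortion. Because the two routes pull the AUC in opposite directions, it could not be corrected afterwards without a record of who saw which prediction and when.

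**Working it through.** **1. The plan's own figures.** Sample size asks for 200 training events at 10 per candidate variable, which implies 200/10 = 20 variables. With the 7:3 split, 200/0.7 = 285.7 (stated as 290). With 100 external events and 20% incidence, (290 + 100)/0.20 = 1950, which reproduces the stated total. The external set at that minimum is 100/0.20 = 500 patients. These figures are not in dispute; they supply the event count and incidence used below.

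**2. The passages side by side.**

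| Question | What the Protocol says |
|---|---|
| Does the data-collection tool produce the risk? | Yes: the same URL validates and collects |
| Are the external patients prospective? | Yes |
| When are data entered, before or after MBE is known? | Not stated |
| Is the output hidden or locked? | Not stated |
| Is whoever determines MBE masked to the predicted risk? | Not stated; the two masking sentences concern other information |
| Are there MBE criteria that limit judgement? | None given |

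Exposure before the outcome is recorded is therefore open, but it is not established.

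**3. Who could be exposed.** The URL exists only after the model is built. If the lead centre's stated minimum is met first, that takes 290/0.20 = 1450 patients there. External patients treated before that point cannot have been affected. The documents do not say how many they will be.

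**4. Illustrative size.** The values in this step are assumed, apart from the 20% incidence. The linear predictor is normal with SD 1.35, the intercept is set to give 20% incidence, and the true AUC is then about 0.80. Patients with predicted risk of 30% or more are 23% of the cohort and hold 56% of the events. Every such patient is taken as exposed.

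- *Care route:* a fraction a of MBE is averted in the high-risk group. Observed/expected = 1 − 0.56a.
  - a = 0.10: 1 − 0.056 = 0.944; AUC about 0.785 (shift −0.015).
  - a = 0.40: 1 − 0.224 = 0.776; AUC about 0.73 (shift −0.07).
- *Labelling route:* a fraction d of high-risk non-events is called MBE, and the same fraction of low-risk events is missed.
  - d = 0.05: AUC about 0.81 (shift +0.01).
  - d = 0.20: AUC about 0.84 (shift +0.04).

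Other assumptions were tried: true AUC 0.742 or 0.808, cut-off 20% or 30%, aversion of 10–30%, drift of 5–10%. The AUC then falls by 0.015 to 0.056 on the care route (observed/expected 0.78–0.95) and rises by about 0.01 to 0.03 on the labelling route (observed/expected 1.00–1.10).

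**5. Sampling error for comparison (Hanley–McNeil).** Take A = 0.80, 100 events and 400 non-events.

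- Q₁ = A/(2 − A) = 0.6667; Q₂ = 2A²/(1 + A) = 0.7111.
- Variance = [0.16 + 99(0.6667 − 0.64) + 399(0.7111 − 0.64)]/40,000 ≈ 0.00078.
- Half-width = 1.96 × 0.0279 ≈ 0.055.

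At 200 events it is about 0.039. With A = 0.75 the two values are 0.059 and 0.042.

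**The case against.** The strongest reply is that entry timing is inferred. The key sentence also fits the entry of completed cases, and the Inclusion and Exclusion Criteria lend that reading support: a patient needs three months of completed follow-up, and those with incomplete data are excluded. Membership of the validation set is then final only long after day 3. Prospective describes how patients accrue, not when the calculator is run. This stands. A reader might infer that sites will run a live bedside tool and see the risk before MBE is determined; the Protocol does not say so. It only fails to rule it out.

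The care route has thin support too. The one intervention named in the Background is early decompressive hemicraniectomy, credited with benefit in patients who already have MBE. No passage describes a treatment that prevents the day-3 outcome, and all patients go to neuro-intensive care with the same CT schedule. A reader might infer that displayed risks would avert a sizeable share of MBE. The documents give no basis for that, and the 10–40% is assumption only.

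The blinding of imaging readers would limit label drift if those readers determine MBE on follow-up CT. But the sentence sits with the baseline imaging predictors, and the Protocol does not say who determines MBE.

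On size, most of the assumed scenarios give shifts below the 0.055 half-width, and only strong aversion reaches or passes it. This stands, with the qualification that a bias, unlike sampling error, does not shrink as events are added.

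Finally, form layout and data locks are often left to a SAP or data-management plan. That would answer a mere omission. Here the Protocol itself assigns data collection to the page that shows the prediction.

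**Conclusion.** The point holds as a weakness in a stated procedure, not as a demonstrated bias. The Protocol uses one web tool to predict, to validate and to collect data on prospective patients, with an outcome that has no written criteria, and nothing in it keeps the prediction from those who treat the patient or determine the outcome. Whether exposure will occur, and in how many patients, cannot be told from the document.

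If it does occur, the external AUC could move by roughly 0.01 to 0.07 in either direction: up to about 0.04 upward through labelling and up to about 0.07 downward through care. Observed/expected could fall to about 0.78 on the care route. These figures assume a true AUC near 0.80, a 30% risk cut-off, the stated 20% incidence, and exposure of every high-risk external patient. Partial exposure would make them smaller. A reader should not infer that the external results will be inflated, or deflated, by any given amount.

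The change is worth making before external data are collected, because it removes both routes whichever reading of entry timing is right.

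**What to change.** Amend the Statistical analysis section as follows.

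1. Outside centres record predictors and MBE status on a form that displays no risk. This can be the registry form, or the web page with its output hidden.
2. Predictions for the external set are computed centrally from the fixed model equation, after each patient's day-3 MBE status is locked. The Protocol already builds the model before deploying it, so only the statement that the equation stays unchanged during validation is new.
3. Whoever determines MBE is masked to the predicted risk; say who that is.
4. The working URL is released to the outside centres once validation is complete.

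If the sponsor already intends entry only after the outcome is known, a sentence saying so, together with item 3, would settle most of the point.

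The cost is protocol wording and one hidden field. No extra patients, staff or procedures are needed, and care is not changed. The small downside is that sites cannot use the tool while it is being validated.

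### The training-set AUC, its 95% CI and the training-set decision curve are used to judge the model, although they are apparent values from the data that selected and fitted it

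*Protocol*

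**What the plan says.** The model is selected and fitted in the training set. Under Study groups, "imaging and clinical parameters will be enrolled into LASSO regression analysis", and after multivariable logistic regression "the results will be used to create a predictive model based on the training set". Under Statistical analysis, variables with P < 0.1 "in univariate analysis will be incorporated into logistic regression analysis using forward stepwise selection method", and factors with P < 0.05 "will be included as independent predictors of MBE in the model".

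The closing part of Statistical analysis then states how performance is judged. The AUC serves to evaluate how well the model can "identify high-risk MBE patients after EVT in the training, internal and external validation sets, and corresponding 95% CIs will be calculated". Decision curve analysis "will determine the clinical net benefit of the model at different risk threshold probabilities in the three sets". The three sets have equal standing. The training values are not called apparent, and no bootstrap, cross-validation or shrinkage step is named.

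**The concern.** An AUC computed in the patients who chose the variables and supplied the coefficients is biased upward as an estimate of how that model ranks new patients. The usual 95% interval allows for sampling error only. It takes the model as given, so it is centred too high and is no wider for the search. The training decision curve shares the bias.

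The protocol does more than leave a detail open. It names the training set as a place where the model's ability and net benefit are determined. At stake is whether a reader of the results, or a user of the web nomogram, takes the training AUC and its interval as what to expect in new patients.

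**Working it through.** **Planned size (Sample size section).**
- 10 events per candidate and 200 training events imply 200 / 10 = 20 candidates. The protocol does not state the number.
- 200 / 0.7 = 285.7, so 286 events at the lead centre; the protocol says 290.
- (290 + 100) / 0.20 = 1,950, the protocol's minimum total. With 200 external events it would be (290 + 200) / 0.20 = 2,450.
- Training: 0.7 × 290 = 203 events, or 203 / 0.20 = 1,015 patients. Internal validation: 0.3 × 290 = 87 events, 435 patients. External: 100 to 200 events, 500 to 1,000 patients.

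The sample-size figure reproduces and is not in question.

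**Simulation.** Each replicate had 1,000 training patients, 20% events, and 20 or 30 candidates. It applied the univariate screen at P < 0.1, forward stepwise entry at P < 0.05, retention at P < 0.05 and a logistic refit. The apparent AUC with its DeLong 95% CI was compared with the same fitted model's AUC in 40,000 new patients. There were 800 replicates per row below, so the Monte Carlo error of a coverage figure is 1 to 2 percentage points. Assumptions not in the protocol: normally distributed predictors, the attainable AUC, and the number and strength of true predictors. The LASSO step was left out.

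| Candidates | True predictors | Attainable AUC | Apparent AUC | True AUC | Excess | Coverage of 95% CI | CI wholly above truth |
|---|---|---|---|---|---|---|---|
| 20 | 6 graded | 0.70 | 0.707 | 0.685 | 0.022 | 79.9% | 19.8% |
| 20 | 6 graded | 0.80 | 0.805 | 0.792 | 0.012 | 85.9% | 13.8% |
| 20 | 6 graded | 0.85 | 0.853 | 0.844 | 0.009 | 88.1% | 11.5% |
| 20 | 10 graded | 0.70 | 0.706 | 0.678 | 0.028 | 71.4% | 28.6% |
| 20 | 10 graded | 0.80 | 0.806 | 0.788 | 0.018 | 78.5% | 21.5% |
| 30 | 6 graded | 0.70 | 0.711 | 0.686 | 0.026 | 72.0% | 28.0% |
| 30 | 6 graded | 0.80 | 0.806 | 0.791 | 0.014 | 83.3% | 16.5% |

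Over all main scenarios (attainable AUC 0.70 to 0.90) the excess was 0.007 to 0.028, against a standard error of 0.011 to 0.020. Coverage was 71 to 88%, and the interval lay wholly above the truth in 11 to 29% of studies, where 2.5% is nominal. Logit-scale intervals covered 74 to 91%. In the mildest cases tried (3 or 5 equally strong predictors, attainable AUC 0.80, 600 replicates) the excess was 0.006 to 0.009 and coverage about 91%. A separate run with 1,015 patients, 20 to 26 candidates and 300 replicates gave an excess of 0.008 to 0.024 and coverage of 71 to 87%.

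**Check by hand.** If the error of the apparent AUC is roughly normal with bias b and standard error s, coverage is about Φ(1.96 − b/s) − Φ(−1.96 − b/s). For 20 candidates, 10 graded predictors and attainable AUC 0.70, b/s = 0.0283 / 0.0203 = 1.39, which gives Φ(0.57) − Φ(−3.35) ≈ 0.71. The simulation gave 71.4%.

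**Decision curve.** At a 20% threshold the training net benefit was too high by 0.002 to 0.009, on true values of 0.05 to 0.125.

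**Held-out data.** The AUC interval in an internal validation set of about 430 patients covered 93 to 95%, with bias of about 0.001 or less. The external set was not simulated, but it plays no part in selection or fitting and cannot carry this bias.

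**Does the correction work?** A bootstrap repeating the simulated selection was tried with 40 resamples and 150 replicates.
- 6 graded predictors, attainable AUC 0.80: apparent 0.805, corrected 0.789, true 0.792; coverage 88.7% before and 91.3% after shifting the interval.
- 10 graded predictors, attainable AUC 0.75: apparent 0.755, corrected 0.731, true 0.733; coverage 74.0% before and 94.7% after.

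**The case against.** The strongest defence is that the plan already holds the honest answer. A random 30% of the lead centre's patients form an internal validation set, other centres form an external one, and the AUC, its interval and the decision curve are reported in both. The protocol assigns validation to those sets and rests no threshold or decision on the training value. The bias is also small in absolute terms, and reporting a training AUC beside validated ones is common. All of this stands and limits the harm. It does not make the training interval a 95% interval for the model's ability, which is the use the protocol states.

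Several stronger readings are tempting and are not supported:
- A reader might infer that optimism will be mistaken for poor transport to other centres. The internal set prevents this: training against internal AUC shows optimism, and internal against external shows transport.
- A reader might infer that the training set must carry the narrowest interval. That is clear only with 100 external events. With 200, the external set (about 1,000 patients) matches the training set (about 1,015).
- A reader might infer coverage as low as 55%. The lowest value in the runs above is about 71%, and the protocol gives no signal strength from which a worse figure could be derived.
- The independent-predictor label and the odds ratios after selection raise a separate variable-selection question. This point does not rest on it.

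An SAP may exist and could set resample counts. The issue here is a use that the protocol itself states, not a detail it leaves out.

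**Conclusion.** The point holds in limited form. Statistical analysis uses the training-set AUC, its 95% CI and the training-set decision curve as measures of ability and net benefit, and these are apparent values. At the planned size the AUC is too high by about 0.01 to 0.03. The nominal 95% interval covers the fitted model's true AUC in about 71 to 88% of studies, or about 91% if a few strong predictors carry all the signal, and nearly all misses are optimistic.

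The direction follows from reusing the data. The size rests on the assumed predictor distributions and signal strength and on a simulation without the LASSO step, so it is a range and not a forecast. The validation estimates are not affected. The harm is confined to training-set figures being read as performance, and the change is worth making because it costs so little.

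**What to change.** In the AUC and decision-curve part of Statistical analysis:
1. Replace the training-set AUC as a performance measure with a bootstrap optimism-corrected AUC. Each resample repeats every selection step: LASSO, univariate screen, forward stepwise and P < 0.05 retention. Shift the interval by the estimated optimism.
2. Label any uncorrected training AUC or decision curve as apparent.
3. State that conclusions on performance and net benefit rest on the internal and external validation sets.

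Steps 2 and 3 alone would remove the misreading; step 1 also gives a usable training estimate. The training decision curve may stay if labelled.

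The cost is computing time and a training AUC about 0.01 to 0.03 lower, with no extra patients or data. The shifted interval ignores the uncertainty in the estimated optimism, so it improves coverage but does not guarantee 95%; the milder test case reached 91.3%.

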The study is a multicenter, prospective, observational clinical registry study, commenced on April 1, 2024, and is expected to end in June 2027. Participants were ALVOS patients undergoing EVT treatment in neurology departments from multiple stroke centers. The data from Zhejiang Provincial People's Hospital compose the model training cohort, while data from other centers serve as an independent external validation cohort. The protocol of the study has been approved by the human Ethics Committee of Zhejiang Provincial People's Hospital (KY2024058). All clinical investigations will be conducted according to the principles set in the Declaration of the Helsinki.

Inclusion Criteria:

- (1) Age > 18 years old;
- (2) Onset of stroke to hospital admission < 24 hours;
- (3) Admission with a head CT scan ruling out hemorrhage;
- (4) Patients undergoing CT perfusion scan before treatment;
- (5) Confirmation of internal carotid artery (ICA) or middle cerebral artery (MCA) occlusion or tandem occlusion by Digital Subtraction Angiography (DSA) and subsequent EVT;
- (6) complete 3-months follow-up.

Exclusion Criteria:

- (1) Poor quality of preoperative CT perfusion imaging;
- (2) Posterior circulation occlusion or isolated anterior cerebral artery occlusion;
- (3) Presence of other severe diseases such as malignant tumors, severe organ failure, or other life-threatening conditions with an expected survival period of less than 90 days;
- (4) Incomplete imaging and clinical data.

Procedures

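### Calibration is planned as plots plus a Hosmer-Lemeshow test, with no estimate that carries a confidence interval; adding calibration intercept and slope with 95% CIs in the two validation sets is a cheap improvement of low severity

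*Protocol*

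**What the plan says.** The Protocol fixes the calibration method in one sentence under Statistical analysis: "Calibration plots and the Hosmer-Lemeshow goodness-of-fit test will assess the consistency between actual MBE occurrence and predicted MBE risk probability in EVT patients". That sentence names no data set. No section mentions a calibration intercept, a calibration slope, an observed/expected ratio or any other calibration estimate with an interval.

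The neighbouring measures are specified more fully. The AUC is to be given with 95% CIs in the training, internal validation and external validation sets. For clinical usefulness, "Decision curve analysis (DCA) will determine the clinical net benefit of the model at different risk threshold probabilities in the three sets".

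The predicted risk is meant for use: once the model is built, "it will be converted into a dynamic nomogram and deployed on a webpage, generating a dynamic nomogram URL". Under Study population, the lead centre supplies the development data, "while data from other centers serve as an independent external validation cohort".

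The size of the validation sets follows from Sample size: at the lead centre "at least 290 MBE patients will be required in this study"; "The external validation set will require 100-200 positive samples"; and in total "this study will need to include at least 1950 EVT patients", at an MBE incidence of about 20%.

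**The concern.** The model will show each patient an absolute risk of MBE, it will be carried to other centres, and net benefit will be read at risk thresholds. All three uses depend on whether a displayed 20% really means 20%. A reader at another centre therefore needs to know how far the predictions are too high, too low or too extreme, and how precisely that is known.

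The plots answer this by eye, without a stated interval. The HL test compares observed and expected events in risk groups and condenses them into a chi-square and a P value. Neither separates over- from underprediction, and neither has a size that can be interpreted. For the same miscalibration, both also shift with the number of patients. A non-significant result in about 100 events leaves moderate miscalibration open.

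**Working it through.** **Set sizes, from the Protocol's own figures (Sample size)**
- Lead centre: 200 training events / 0.7 = 285.7, stated as 290.
- Total: (290 + 100) / 0.20 = 1950, which reproduces the stated minimum. With 200 external events it would be (290 + 200) / 0.20 = 2450, so 1950 rests on the lower end of the external target.
- External minimum: 290 / 0.20 = 1450 patients at the lead centre; 1950 - 1450 = 500 patients; 500 × 0.20 = 100 events.
- Internal validation: 0.30 × 1450 = 435 patients; 435 × 0.20 = 87 events.

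**Assumptions not in the Protocol.** Normally distributed linear predictor (LP), AUC about 0.73-0.85, the miscalibration sizes below, tests at 5%, and HL with 10 groups on 10 df. Ten df hold the test's size in validation data. With the development-data convention of 8 df, a perfectly calibrated model would be rejected in about 10-13% of runs.

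**Quantities**
- HL = sum over groups of (O - E)² / [E(1 - E/n)].
- Calibration intercept a: logit P(MBE) = a + LP, with LP as offset; ideal value 0.
- Calibration slope b: logit P(MBE) = c + b × LP; ideal value 1.

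**Simulated detection at 500 patients, 100 events**

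| True error | HL | Intercept or slope test |
|---|---|---|
| Mean prediction 24%, true 20% | about 17-24% | intercept: about 63-73% |
| Mean prediction 16%, true 20% | about 47-55% | intercept: about 70-80% |
| Slope 0.8 | about 23-43% | slope: 39-54% (AUC 0.73-0.80) |

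In one rerun HL reached 56% for slope 0.8, at AUC about 0.85. In that set-up the slope error also raised the mean prediction to 23%, so two errors were present together.

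**Check by formula at the lower AUC**
- Mean 24%: true intercept -0.27, standard error 0.119; 0.27 / 0.119 = 2.27; Φ(2.27 - 1.96) = Φ(0.31) = 0.62, near the lower end of the simulated range.
- Slope 0.8: standard error 0.117; 0.20 / 0.117 = 1.71; Φ(1.71 - 1.96) = Φ(-0.25) = 0.40, against 0.39 simulated.

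**What the estimates add after a non-significant HL** (500 patients, AUC 0.73-0.80). With mean prediction 24%, the intercept CI still excludes 0 in about 55-61%. With slope 0.8, the slope CI excludes 1 in about 28-36%.

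**Dependence on set size** (AUC 0.73-0.80). For the same overprediction (24% against 20%), HL detects about 17-22% at 500 patients and about 48-54% at 1,000.

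**Where HL does better.** With an omitted quadratic term of 0.2, 0.3 or 0.4 on the logit scale, HL at 500 patients detects 19%, 35% and 60%. A joint 2-df intercept/slope test detects only 6-7%.

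**Precision of the added estimates** (95% CI half-widths, true slope 1)
- External, 500 patients: intercept about ±0.23 to 0.26, slope about ±0.21 to 0.29.
- Internal, 435 patients: intercept about ±0.25 to 0.28, slope about ±0.23 to 0.31.

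**The case against.** The strongest reply is that nothing planned is wrong. The plots are appropriate and already show direction and rough size, HL has a use, and a SAP that is not shown could add further statistics. This stands in part and is why the severity is low. It does not remove the point: the Protocol itself names the calibration measures, and none of them comes with an interval, although the AUC beside them does.

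A reader might infer more than the documents support:
- *That a P value is the only numeric output.* HL also yields a chi-square, built from observed and expected counts by risk group. The supported complaint is that no calibration estimate with a CI is planned.
- *That HL usually misses mild to moderate miscalibration.* This is one-sided. It fits overprediction, but underprediction of similar size is found about half the time, and severe error is mostly detected: a slope of 0.6 in 89-97% and a mean prediction of 28% in 83-88% at 500 patients (AUC 0.73-0.80).
- *That the Protocol treats a non-significant HL as proof of good calibration.* It states no such rule.
- *That HL alone causes the low power.* Set size contributes: the joint intercept/slope test detects slope 0.8 in only 30-43%, against 23-36% for HL (AUC 0.73-0.80).
- *That a bootstrap in the development data is needed.* No defect is shown there that this point must repair, and the internal validation set already checks the model. Such a bootstrap would also depend on whether selection follows Study groups ("imaging and clinical parameters will be enrolled into LASSO regression analysis") or the univariate screen and stepwise selection under Statistical analysis, which is a separate question.

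**Conclusion.** The point holds as a cheap improvement of low severity. That an HL statistic or P value carries no direction, no interpretable size and no interval needs no simulation. The size of the gain does rest on assumptions: 20% incidence from the Protocol, and an assumed AUC of about 0.73-0.85, 10 groups and 10 df. On these, the gain at 100 external events is largest for a shift in mean risk and modest for slope, while HL remains the better tool for curvature. It would be wrong to conclude that the plan miscalculates or contradicts itself, or that HL should be removed. Sample size, endpoint and model are unaffected.

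**What to change.** Amend the calibration sentence, or settle it in the SAP, as follows:
- Name the sets in which calibration is assessed, as is done for the AUC and decision curves.
- Keep the calibration plots and add a smoothed curve.
- Report the calibration intercept (calibration-in-the-large) and calibration slope with 95% CIs in the internal and external validation sets, as the main numeric calibration measures. They tell nothing in the training set, where a maximum-likelihood logistic fit gives 0 and 1 by construction.
- Keep HL as a supplementary goodness-of-fit test.

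The cost is a small text change and two logistic fits per validation set, with no extra patients or data. The downside is that with about 100 events the intervals will be fairly wide, and the report will show it.
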